### **3.5.6 PHASE II (PART 2) EXCLUSION CRITERIA**

Subjects are required to meet NONE of the following criteria for randomization into the Phase II (Part 2) of the study:

1. Pregnant or lactating females or women who are planning for pregnancy in the next 6 months
2. Women at postpartum for 3 months or less prior to screening
3. Serious medical illnesses such as end-stage renal disease, liver failure or heart failure that, in the opinion of the Investigator may interfere with the conduct of the study
4. Subjects with abnormal vital signs, physical and dermatological exams or clinical laboratory evaluations considered clinically significant by the Principal Investigator, which in the opinion of the PI would significantly interfere with the study conduct
5. Subjects with any concurrent skin condition that could interfere with the evaluation of the treatment areas, as determined by the investigator
6. The subject has a planned major surgical intervention for a pre-existing condition within the duration of the study
7. The subject has a history of drug or alcohol abuse that would impair or risk the subject's full participation in the study, in the opinion of the investigator.

8. Participation in a clinical trial within 3 months, or more than two clinical trials within 12 months prior to screening
9. Concurrent or recent use of prescription moisturizers, topical steroids, topical immunosuppressive/immunomodulative drugs, topical vitamin D3 derivative, topical retinoids, anthralin, coal tar (except when used as shampoo) or salicylic acid within 14 days of the baseline visit
10. The subject has severe AD as determined by vIGA-AD™ score higher than 3
11. The subject cannot avoid systemic treatments (including systemic corticosteroids, immunotherapy, biologics or phototherapy) for AD during the study per the Investigator
12. The subject has previously received any systemic treatments, immunotherapy, biologics or phototherapy for AD within 12 months prior to study enrollment
13. Current or expected use of prohibited medications and procedures during study treatment, as described in [Section 7](#), unless approved by the study Medical Monitor
14. Subject has unstable AD or any consistent requirement for high-potency topical corticosteroids to manage AD signs and symptoms
15. Subject has a significant active systemic or localized infection, including known actively infected AD
16. Regular use (more than 2 visits per week) of a tanning booth/parlor within 4 weeks of the screening visit
17. The subject has previously received AMTX-100 *CF*
18. Subject has any other medical or psychological condition (including relevant laboratory abnormalities at screening) that, in the opinion of the investigator, may suggest a new and/or insufficiently understood disease, may present an unreasonable risk to the study patient as a result of his/her participation in this clinical trial, may make patient's participation unreliable, or may interfere with study assessments.
19. The subject has concurrent contact dermatitis; or history of anaphylactic reaction.

## 4 STUDY SCHEDULE

The schedules for the protocol-specified assessments and procedures for Phase I (Part 1) and Phase II (Part 2) of this study are detailed in this section. Day 0 is used as the day of baseline/randomization and first study treatment administration in both parts of the study. See [Table 4-1: Phase I \(Part 1\) - Study Schedule of Events](#) and [Table 4-2: Phase II \(Part 2\) - Study Schedule of Events](#).

**Table 4-1: Phase I (Part 1) - Study Schedule of Events**

Visit		Visit 1 (Screening)	Visit 2 (Phone call)	Visit 3 (Baseline)	Visit 4 (End of Treatment)	Visit 5 (Follow Up)
Days From Randomization		Up to -21 days	Up to -7 days	Day 0	Day +7	Day +21
Weeks From Randomization		Week -3	Week -1	Week 0	Week 1	Week 3
Window Period			±2 days			±2 days
	Protocol Section					
		X				
		X	X			
		X				
		X				
		X		X 		
		X		X 	X	X
		X				
		X		X 	X	X
		X		X 	X	X
		X		X 	X	X
		X		X 	X	X
			X			
				X		
				2 nd dose (PM) on Day 0, then BID through Day 6		
				X 	X	
					X	
				X 	X	X

**Table 4-2: Phase II (Part 2) - Study Schedule of Events**

Visit		Visit 1 (Screening)	Visit 2 (Baseline/ Randomization )	Visit 3	Visit 4	Visit 5	Visit 6 (End of Treatment)	Visit 7 (Follow Up)
Days From Randomization		Up to -28 days	Day 0	Day +7	Day +14	Day +21	Day +28	Day +42
Weeks From Randomization		Week -4	Week 0	Week 1	Week 2	Week 3	Week 4	Week 6
Window Period				±1 days	±1 days	±1 days	±1 days	±3 days
	Protocol Section							
		X						
		X	X 					
		X						
		X	X 					
		X	X 	X	X	X	X	X
		X						
		X	X 		X		X	X
		X	X 	X	X	X	X	X
		X	X 		X		X	X
			X 		X		X	X
			X 		X		X	X
		X	X 		X		X	X
			X 		X		X	X
		X	X 				X	X
			X 		X		X	X

Visit		Visit 1 (Screening)	Visit 2 (Baseline/ Randomization )	Visit 3	Visit 4	Visit 5	Visit 6 (End of Treatment)	Visit 7 (Follow Up)	
Days From Randomization		Up to -28 days	Day 0	Day +7	Day +14	Day +21	Day +28	Day +42	
Weeks From Randomization		Week -4	Week 0	Week 1	Week 2	Week 3	Week 4	Week 6	
Window Period				±1 days	±1 days	±1 days	±1 days	±3 days	
	Protocol Section								
		X	X 	X	X	X	X	X	
		X	X 	X	X	X	X	X	
		X	X	X	X	X	X	X	
			X 		X		X		
			X						
			X 	X	X	X			
			X 						
			2 nd dose (PM) on Day 0, then BID through Day 27						
		Twice daily (no earlier than 1 hour before or after the study treatment administration), starting at least 1 week immediately before the baseline visit (Visit 2, Day 0) and continued throughout the study							
		X	X 	X	X	X	X		
			X	X	X	X	X	X	
				X	X	X	X		
			X 	X	X	X	X	X	
			X 	X	X	X	X	X	

Visit		Visit 1 (Screening)	Visit 2 (Baseline/ Randomization )	Visit 3	Visit 4	Visit 5	Visit 6 (End of Treatment)	Visit 7 (Follow Up)
Days From Randomization		Up to -28 days	Day 0	Day +7	Day +14	Day +21	Day +28	Day +42
Weeks From Randomization		Week -4	Week 0	Week 1	Week 2	Week 3	Week 4	Week 6
Window Period				±1 days	±1 days	±1 days	±1 days	±3 days
	Protocol Section							

- █ [REDACTED]
- █ [REDACTED]
- █ [REDACTED]

#### 4.1.5 PHASE I (PART 1) - VISIT 5: FOLLOW UP (WEEK 3: DAY 21±2)

After completion of Visit 4 procedures, subject will be followed up 14 days to assess safety and tolerability of topically applied AMTX-100 *CF*. The following assessments will be performed:

- █ [REDACTED]

#### 4.2 PHASE II (PART 2) STUDY VISITS

##### 4.2.1 PHASE II (PART 2) - VISIT 1: SCREENING VISIT (UP TO -28 DAYS)

The subject will sign and date the ICF, and Health Insurance Portability and Accountability Act (HIPAA) authorization (according to site practices) prior to any study-related procedures. A subject number will be assigned to each subject in successive order of consent signing at each center, beginning with 01 at each site. Each study site will receive a unique numeric designation, and will precede the subject number (e.g. at study center 01 the first two consented subjects would be 01-001 and 01-002; at study center 02 the first two consented subjects would be 02-001 and 02-002).

Screening Visit procedures of Phase II (Part 2) of the study are per below:

- █ [REDACTED]
- █ [REDACTED]
- █ [REDACTED]
- █ [REDACTED]

- █ [REDACTED]
- █ [REDACTED]
- █ [REDACTED]
- █ [REDACTED]
- █ [REDACTED]
- █ [REDACTED]
- █ [REDACTED]
- █ [REDACTED]
- █ [REDACTED]
- █ [REDACTED]
- █ [REDACTED]
- █ [REDACTED]
- █ [REDACTED]
- █ [REDACTED]
- █ [REDACTED]
- █ [REDACTED]
- █ [REDACTED]

**4.2.3 PHASE II (PART 2) - VISIT 3 (WEEK 1: DAY 7±1)**

The following assessments will be performed:

- █ [REDACTED]

- █ [REDACTED]
- █ [REDACTED]
- █ [REDACTED]
- █ [REDACTED]
- █ [REDACTED]
- █ [REDACTED]
- █ [REDACTED]
- █ [REDACTED]
- █ [REDACTED]
- █ [REDACTED]
- █ [REDACTED]
- █ [REDACTED]
- █ [REDACTED]
- █ [REDACTED]
- █ [REDACTED]

**4.2.6 PHASE II (PART 2) - VISIT 6: END OF TREATMENT (WEEK 4: DAY 28±1)**

The following assessments will be performed:

- █ [REDACTED]

- █ [REDACTED]
- █ [REDACTED]
- █ [REDACTED]
- █ [REDACTED]
- █ [REDACTED]
- █ [REDACTED]
- █ [REDACTED]
- █ [REDACTED]
- █ [REDACTED]

**4.2.7 PHASE II (PART 2) - VISIT 7: FOLLOW UP (WEEK 6: DAY 42±3)**

After completion of Visit 6 procedures, subject will be followed up 14 days to assess safety and tolerability of topically applied AMTX-100 CF3. The following assessments will be performed:

- █ [REDACTED]

█ [REDACTED]

█ [REDACTED]

█ [REDACTED]

### 4.3 UNSCHEDULED VISITS

Unscheduled visits may be required in addition to the scheduled visits per the Investigator's discretion. The details of these unscheduled visits with subjects will be recorded in the medical records and on the electronic Case Report Form (eCRF).

### 4.4 MISSED VISITS

If a subject misses a visit, the site is to make every effort to have the subject return as soon as possible to make up the visit. Once the subject is seen, he/she is to return to his/her original visit schedule.

## 5 SUBJECT COMPLETION AND WITHDRAWAL, STUDY EARLY DISCONTINUATION

### 5.1 SUBJECT COMPLETION

[REDACTED]

### 5.2 SUBJECT PREMATURE WITHDRAWAL FROM THE STUDY

[REDACTED]

Reasons for subject withdrawal/discontinuation may constitute one of the following:

- Subject chooses to withdraw
- Subject is withdrawn due to an AE
- Pregnancy or positive pregnancy test
- Lost to follow-up
- The Investigator determines that it is in the subject's best interest
- Excessive protocol deviations, as determined by the Investigator or the Sponsor

- Discontinuation of the study by the Sponsor

[REDACTED]

- [REDACTED]
- [REDACTED]
- [REDACTED]

**Important Notes:**

1. Subjects may drop out or be withdrawn at their own request. Although subjects do not need to give a reason for requesting withdrawal from the trial, the Investigator should make a reasonable effort to ascertain the reason(s), while fully respecting the subject's rights.
2. Any subjects reporting Serious Adverse Events (SAEs) that have not been resolved by their last study visit will be followed to resolution or until 30 days after the subject completes the study.
3. Every attempt should be made to collect follow-up information. The reason for withdrawal from the study (if known) will be recorded in the source documents and on the appropriate page of the eCRF.
4. Before a subject is identified as lost-to-follow-up, the site should make all reasonable efforts to contact the subject. These attempts must be documented and should include at a minimum one phone call and one follow-up letter.

**5.3 SCREEN FAILURES**

A subject who has signed the consent form but is not randomized is classified as a screen failure. The screen failure must be entered into the study eCRFs. Subject number, demographic information, and reason for screen failure will be collected. If a subject initially fails to meet inclusion/exclusion criteria and is later reconsidered for participation, the subject can be re-consented only once more, at least 30 days after the initial screening. The subject will need to be re-consented in such a case and will be assigned a new screening number at the time of re-screening.

**5.4 EARLY DISCONTINUATION OF THE CLINICAL TRIAL**

[REDACTED]

- [REDACTED]

█ [REDACTED]

[REDACTED]

## 6 STUDY TREATMENTS

### 6.1 METHOD FOR ASSIGNING ELIGIBLE SUBJECTS TO TREATMENT

In Part 1 of the study, study eligible subjects will be assigned to open-label AMTX-100 CF (in 1.1% concentration), based on a cohort assignment schedule prepared by the contracted CRO. Details of the cohort assignment and assignment of the subject number are provided in [Section 8.11](#) and [Section 4.1.1](#).

Subjects in Part 1 of the study will be assigned sequentially to one of the following treatment groups:

█ [REDACTED]

█ [REDACTED]

█ [REDACTED]

█ [REDACTED]

█ [REDACTED]

After a subject has been determined to be eligible for the treatment in Part 1 of the study, a cohort assignment number will be assigned. Once the cohort assignment number is assigned, it cannot be re-assigned even if the subject is subsequently deemed ineligible or withdraws consent.

[REDACTED]

In Part 2 of the study, study eligible subjects will be randomized based on a randomization schedule prepared by the contracted CRO. Details of the randomization and assignment of the subject number are provided in [Section 8.12](#) and [Section 4.2.1](#).

Subjects will be randomized in a 1:1 ratio to one of the following treatment groups in Part 2 of the study:

- Active Treatment (Group A): AMTX-100 CF3 (1.1% w/w);
- Placebo (Group B): Vehicle ( 0% w/w)

After a subject has been determined to be eligible for the treatment in the study, a randomization number will be assigned. Once the randomization number is assigned, it cannot be re-assigned even if the subject is subsequently deemed ineligible or withdraws consent.

[figure not shown]
## 6.2 STUDY TREATMENT DESCRIPTION

[figure not shown]
Test treatment for this trial is AMTX-100 CF3. AMTX-100 CF3 is a water-based, white topical cream that will be administered to the AD-affected area twice daily for 7 days (total 14 applications) during Part 1 of this study and for 28 days (total 56 applications) during Part 2 of this study.

AMTX-100 CF3 formulation dose per area of skin is 0.002575 g/cm^2 in humans.

AMTX-100 CF3 formulation will be provided in 1.1% w/w concentration.

[figure not shown]
The ingredients in each are included in [Table 6-1](#) below. Inactive ingredients used in the manufacturing of the drug product are of pharmacopeial quality.

[figure not shown]

### **6.3 STUDY TREATMENT LABELING AND PACKAGING**

Study treatment tubes and cartons will be provided under appropriate investigational product labeling.

[figure not shown]
#### 6.4 STUDY TREATMENT STORAGE

#### 6.5 STUDY TREATMENT ADMINISTRATION

Detailed guidelines for dose of formulation, administration technique and administration direction can be found in the study pharmacy manual.

In Phase I (Part 1) of study, application areas will be all treatable areas, excluding the scalp, face, eyes, eyelids, neck, hands, palms, feet, groin, genitals or in the axillae. The applied amount of AMTX-100 *CF* formulation to the affected assigned areas will depend on the percentage of the BSA affected with AD, as assessed by the investigator, and per the formulation dosing tables in the protocol (refer to [Table 6-3](#)).

[figure not shown]
[REDACTED]	[REDACTED]	[REDACTED]	[REDACTED]
[REDACTED]	[REDACTED]	[REDACTED]	[REDACTED]
[REDACTED]	[REDACTED]	[REDACTED]	[REDACTED]
[REDACTED]	[REDACTED]	[REDACTED]	[REDACTED]
[REDACTED]	[REDACTED]	[REDACTED]	[REDACTED]
[REDACTED]	[REDACTED]	[REDACTED]	[REDACTED]

[REDACTED]	[REDACTED]	[REDACTED]	[REDACTED]
[REDACTED]	[REDACTED]	[REDACTED]	[REDACTED]

In Phase II (Part 2) of the study, application areas will be all treatable lesions of AD, excluding the scalp, face, eyes, eyelids, hands, palms, feet, groin, genitals or the axillae. The applied amount of AMTX-100 CF3 formulation to the affected assigned areas will depend on involvement percentage of treatable BSA, as assessed by the investigator, and per the formulation dosing tables in the protocol and formula of study treatment administration (refer to [Table 6-4](#)).

- [REDACTED]

[REDACTED]

## 6.6 STUDY TREATMENT DISPENSATION

In Part 1 of the study, subjects will be assigned in the designated cohort (dose level) at the time of screening, using an Interactive Web Response System (IWRS) and each subject enrolled into the study will receive assigned number of study treatment tubes with specific tube serial number via IWRS, per the study cohort assignment scheme and Part 1 study treatment assignment chart (Refer to [Table 6-2](#) and [Table 6-3](#)). Site study coordinator or designated site personnel will dispense assigned study treatment tubes to subject in a carton. The subject will receive sufficient instructions on study drug administration compliance and accountability per the above sections.

In Part 2 of the study, subjects will be randomized using a web-based randomization system (IWRS) and each subject enrolled into the study will receive assigned number of study treatment tubes with specific tube serial number via IWRS per the study randomization scheme and Part 2 Dosing Chart (refer

to Table 6-4). The subject will receive sufficient instructions on study drug administration compliance and accountability per the above sections.

### **6.7 STUDY TREATMENT ACCOUNTABILITY**

Study treatments must be used in accordance with this protocol and only under the direction of the responsible investigator. The investigational site must maintain complete and accurate records showing receipt and disposition of all study treatments, including master records listing the date of receipt, the number of the kits received, and a dispensing record which includes each quantity dispensed, identification of the staff member to whom dispensed, the date of dispensing, the intended study participant subject number, and the identification of the preparer. All used and unused study kits will be retained by the investigational site until study treatment accountability can be confirmed by study CRA during the monitoring visits. Instructions will be provided by Sponsor regarding final disposition of all study drug in compliance with applicable regulations.

A study treatment accountability log will be provided to the site for use by the Investigator to maintain current and accurate inventory records (batch, expiry, and quantity) covering the receipt, dispensing and the return/destruction of all the study treatments.

At the conclusion of the study, the Investigator must agree to return or destroy all study materials as instructed by the Sponsor.

### **6.8 STUDY TREATMENT COMPLIANCE**

## 7 CONCOMITANT AND PROHIBITED MEDICATIONS AND FOODS

Subjects must be questioned at each study visit concerning any new medications or changes in current medications including over-the-counter medication and topical medication.

All medications and therapies administered or taken by the subject will be recorded in the source documents and on the appropriate page of the eCRF per below:

- [REDACTED]
- [REDACTED]
- [REDACTED]

- [REDACTED]

[REDACTED]

[REDACTED]

[REDACTED]

- [REDACTED]
- [REDACTED]
- [REDACTED]
- [REDACTED]
- [REDACTED]
- [REDACTED]
- [REDACTED]
- [REDACTED]
- [REDACTED]
- [REDACTED]
- [REDACTED]

For each medication and non-study treatment, the following will be documented:

- Medication/treatment name (generic name may be used if trade name is unknown)
- Dose, unit, and frequency of dosing (individual dosages, not total daily dose). Note: Each new dose of medication should be recorded as a separate entry, with the exception of medications that are given on a sliding scale. For these, it is acceptable to enter the range of the dosage, including the start and stop dates for which the specified dosage range was used.
- Route of dosing
- Indication for use
- The start date
- The stop date (if medication/therapy is not ongoing)

During the study, the subjects will not have any food restrictions, unless food items known to the subject/Investigator to trigger AD symptoms.

## 8 DESCRIPTION OF PROTOCOL ASSESSMENTS AND PROCEDURES

[figure not shown]
### 8.1 INFORMED CONSENT

[figure not shown]
Written informed consent will be obtained for this study by the Investigator or suitably qualified designee from all subjects before the performance of any protocol-specific procedure. This study will be conducted in accordance with the provisions of the Declaration of Helsinki.

In obtaining and documenting informed consent, the Investigator must comply with applicable regulatory requirements and must adhere to GCP. The Investigator, or designee, must fully inform subjects of all pertinent aspects of the study. Before informed consent may be obtained, the Investigator, or a person designated by the Investigator, must provide the subject ample time and opportunity to inquire about details of the study and to decide whether or not to participate in the trial. All questions about the trial must be answered to the satisfaction of the subject. Prior to the subject's participation in the trial, the written informed consent must be signed and personally dated by the subject and by the person who conducted the informed consent discussion.

### 8.2 ELIGIBILITY ASSESSMENT

The eligibility assessment will be done as per inclusion and exclusion criteria of this Protocol as described in [Sections 3.5.3](#) and [3.5.4](#) for Phase I (Part 1) of the study and in [Sections 3.5.5](#) and [3.5.6](#) for Phase II (Part 2) of the study. Diagnosis of atopic dermatitis (AD) will be based on subjects' medical history and records, and confirmed by the Investigator through physical exam, per the Eichenfield revised criteria of Hannifin and Rajka (Eichenfield, 2014) (refer to text [Table 8-1](#)), and through Validated Investigator's Global Assessment for Atopic Dermatitis (vIGA-AD™).

### **8.3 SUBJECT DEMOGRAPHICS**

For the purposes of this study, demographic information will include:

- Date of birth
- Gender
- Race (American Indian/Alaskan Native, Asian, Black/African American, Native Hawaiian/Pacific Islander, Caucasian, or other)
- Ethnicity (Hispanic/Latino or Not Hispanic/Latino)

### **8.4 MEDICAL HISTORY**

All ongoing and any prior medical conditions that have resolved in the past year will be recorded at the Screening Visit (Visit 1).

Events that are reported prior to the first study treatment administration will be recorded as part of the medical history and not as AEs. Aside from being used to determine subject eligibility, this information will permit the Investigator to record the nature, duration and severity of any ongoing baseline medical conditions prior to receiving study treatment.

Medical histories will be recorded using the body system categories outlined below:

- Cardiovascular
- Lymphatic
- Respiratory
- Hematologic
- Gastrointestinal
- Immunologic
- Renal
- Dermatologic
- Hepatic
- Psychiatric
- Neurological
- Genitourinary
- Endocrine
- Other

For each relevant history, the following will be documented:

- Disease/disorder/condition
- Date of onset/diagnosis
- History status (resolved or ongoing)
- Date of resolution, if applicable

Subject's history of AD will be recorded in the Screening eCRF in more details per below:

- Age of onset
- Age of diagnosis
- Treatable % Total Body Surface Area (BSA) with active AD (Refer to [Section 8.13](#))
- Treatments or procedures received for AD:
  - Within 90 days prior to Screening for topical steroids, topical immunosuppressive/immunomodulative drugs, topical vitamin D3 derivative, topical retinoids, anthralin, coal tar (except when used as shampoo) or salicylic acid
  - Within 12 months prior to Screening for systemic treatments, immunotherapy, biologics or phototherapy

## 8.5 VITAL SIGNS

The following vital signs will be collected in the CRF and should be in the subject's medical records:

- Blood Pressure (systolic and diastolic)\*
- Heart Rate (HR)
- Respiration Rate (RR)
- Temperature

*\*Note: Blood Pressure will be assessed in "Sitting Position" after 5 minutes' rest.*

## 8.6 HEIGHT, WEIGHT, BMI AND BSA

Measurements will be taken in street clothing with jacket/coat and shoes removed. Body Mass Index (BMI) will be calculated from the height and weight measurements using the following formulas:

- Metric:  $BMI = \text{Weight (kg)} / [\text{Height (m)}]^2$   
Or,
- Imperial:  $BMI = \text{Weight (lb)} / [\text{Height (in)}]^2 \times 703$

Total Body Surface Area (BSA) will be calculated from the height and weight measurements using the following Mosteller formula (part 1 only):

- $BSA(m^2) = \sqrt{\frac{\text{Height (cm)} \times \text{Weight (kg)}}{3600}}$

## 8.7 PHYSICAL EXAM

The physical examination will include routine examinations, including dermatologic examination, but not including rectal or genitourinary examinations. All clinically significant abnormalities will be recorded in subject's medical record and on the physical exam CRF page. Any abnormality that, in the opinion of the Investigator, is relevant to the safety of the subject or could impact safety or efficacy results for the subject will be considered as "clinically significant". After administration of the first dose of study treatment, each physical exam abnormality that is clinically significant will be recorded as an AE.

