### **8.10 ELECTROCARDIOGRAM (ECG)**

A standard 12-lead ECG will be performed per the site standard procedures. The following parameters will be recorded (as part of the subject's medical record) and recorded on the appropriate page of the CRF: ventricular rate (beats per minute), PR interval (msec), QRS interval (msec), QT interval (msec), and QTc interval (msec). Additionally, the Investigator will record the overall results of the ECG reading as either normal or abnormal, and if abnormal, as either "not clinically significant" or "clinically significant." If abnormalities are observed, each will be recorded. Each treatment-emergent abnormality that is clinically significant will be recorded as an AE. Each ECG should be signed by a physician.

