### 10.1 ADVERSE EVENTS

An adverse event (AE) is defined as any unfavorable or unintended sign, symptom, or disease that occurs or is reported by the subject to have occurred, or a worsening of a pre-existing condition. An AE may or may not be related to the study treatment.

AEs will be elicited through direct questioning and subject reports. Any abnormalities in visit evaluations, physical examination findings or laboratory results that the Investigator believes are clinically significant to the research subject and that occurred after initiation of the first study treatment will be reported as AEs. Abnormal findings that are NOT clinically significant should not be recorded as an AE.

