#### 10.1.7 EXPECTED /ANTICIPATED ADVERSE EVENTS

#### 10.1.8 APPLICATION SITE REACTIONS

For this population, presence of signs/symptoms similar to application site reactions at the eczema lesions at the baseline is expected. Only significant worsening of these signs/symptoms from the baseline per the investigator would be considered adverse events.

[REDACTED]

[REDACTED]

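### Section 8.7 makes clinically significant post-dose physical exam findings AEs without requiring them to be new or worse than baseline, which conflicts with the AE definition in Section 10

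*Protocol*

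**What the plan says.** Protocol Section 8.7 sets three things in sequence.

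- Scope: "The physical examination will include routine examinations, including dermatologic examination".
- Clinical significance: a finding qualifies if, in the investigator's opinion, it bears on the subject's safety or it "could impact safety or efficacy results for the subject will be considered as" clinically significant.
- Recording rule: "After administration of the first dose of study treatment, each physical exam abnormality that is clinically significant will be recorded as an AE".

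Other parts of the protocol attach a condition about timing or change.

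- Section 10.1, on what an AE is, brings in existing disease only through "or a worsening of a pre-existing condition". It names physical examination findings and limits them to clinically significant ones "that occurred after initiation of the first study treatment will be reported as AEs".
- Section 10.1.8 says that "presence of signs/symptoms similar to application site reactions at the eczema lesions at the baseline is expected", and then: "Only significant worsening of these signs/symptoms from the baseline per the investigator would be considered adverse events".
- Section 8.10, the parallel rule for the ECG, reads: "Each treatment-emergent abnormality that is clinically significant will be recorded as an AE".
- Section 8.4 sends events reported before the first dose to medical history rather than to the AE record.

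**The concern.** Section 8.7 is the only one of these rules with no link to the pre-dose state. In a skin disease trial that matters more than usual. Inclusion criterion 9 in both parts requires a vIGA-AD score of 2 or 3 at baseline, so every subject starts with an abnormal dermatologic exam. The reference in 8.7 to efficacy results is wide enough to take in the lesions under treatment, since the Part 2 primary outcome is a vIGA-AD response. The same gap applies to any other exam finding that was present before dosing.

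Two things are at stake. The first is consistency: the same unchanged finding can be entered as an AE at one site and not at another. The second is TEAE incidence, a listed safety outcome in both parts (Protocol 9.2.1.2 and 9.2.2.4; SAP 2.6.1.2).

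**Working it through.** The plan gives no figure on this point, so the check is mainly a comparison of rules applied to one case.

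**Case.** A subject has vIGA-AD 3 at baseline. At a post-dose exam the lesions are unchanged, and the investigator judges them clinically significant under 8.7.

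| Rule | Condition | Is the unchanged lesion an AE? |
|---|---|---|
| 8.7 | Clinically significant; seen after first dose | Yes |
| 10.1, exam findings | Clinically significant; arose after first treatment | No |
| 10.1, existing conditions | Must have worsened | No |
| 10.1.8 | Significant worsening from baseline, for signs resembling application site reactions | No, for those signs |
| 8.4 | Event reported before first dose | No; medical history |

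Section 8.10 does not govern skin findings. It shows that the qualifier missing from 8.7 was written into a neighbouring rule of the same form, which points to a drafting gap.

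**Does anything settle the conflict?** Section 8.7 contains no cross-reference to Section 10, and no visible text says which section prevails.

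**From an AE entry to a TEAE.** Protocol 9.14 and SAP 8.2.1 define a TEAE by onset on or after first treatment, and Protocol 10.1.1 requires an onset date for each AE. Two routes follow.

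- Onset dated before the first dose: the entry is not a TEAE. It still appears in the AE listings, which under SAP 8.2.1 cover all AEs in the eCRF for Part 1.
- Onset dated at the post-dose exam: the entry is a TEAE.

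**Size of one misdated entry**, if the subject has no other TEAE:

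- Part 1 cohort, 5 subjects (Protocol 9.3): 1/5 = 20 percentage points.
- Part 2 arm, 60 subjects randomised 1:1, so 30 per arm (Protocol 3.3): 1/30 = 3.3 percentage points.

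**Scope for inconsistency.** Part 2 may use up to 20 centres for 60 subjects (Protocol 3.5.1). If all 20 take part, that averages 60/20 = 3 subjects per centre, so the recording rule would be interpreted separately at many small sites.

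**The case against.** The strongest reply is that 8.7 describes an assessment while Section 10 defines an AE. Section 10 opens by making the investigator responsible for events that meet the AE definition, and 10.1 deals with physical examination findings by name. Read together with 8.4, the protocol points away from recording unchanged disease. That is a fair reading and probably what was intended. It does not remove the problem, because the 8.7 sentence is unqualified and a site that follows it is following the protocol.

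Other limits also stand.

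- Clinical significance is the investigator's judgement. A reader might infer that persisting atopic dermatitis automatically becomes an AE. The documents do not support that: 8.7 permits the result and its wording invites it, but a judgement comes first.
- The disease must have been confirmed for at least 6 months before enrolment (inclusion criterion 8 in both parts), so a correctly dated entry fails the TEAE definition. Nothing visible tells a site to use the exam date as onset.
- Section 10.1.8 covers only signs that resemble application site reactions, so its conflict with 8.7 is confined to those. Section 10.1 supplies the general conflict.
- Section 10.1.7 shows no text, text after the visible part of 10.1.8 is blacked out, and the schedule tables have lost their row labels. Further handling of disease findings could be in the hidden text, and the visits at which the exam is done cannot be read. The conflict rests only on complete visible sentences.
- TEAEs are tabulated by system organ class and preferred term, so a cluster of dermatitis entries would be noticeable.

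**Conclusion.** The conflict holds on the wording. For the same pre-existing finding, 8.7 and Section 10 can give opposite answers, and nothing visible resolves it. The consequence is inconsistent AE recording between sites. TEAE incidence is inflated only where an unchanged finding is judged clinically significant, entered as an AE under 8.7, and given a post-dose onset date. One such entry can then add 20 points in a Part 1 cohort or 3.3 points in a Part 2 arm.

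A reader might go further and infer a bias between arms: uncleared disease would be commoner on vehicle if the drug works, so active treatment would look safer. The documents do not support putting a size or direction on that. They give no clearance rates for either arm. The inference would also need investigators generally to take the literal reading, judge residual disease significant and date its onset after dosing.

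Wrong as written; minor severity.

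**What to change.** Reconcile 8.7 with Section 10 by replacing its last sentence with:

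*After the first dose of study treatment, each clinically significant physical exam abnormality that is new or has worsened since the pre-dose baseline exam will be recorded as an AE (see 10.1 and 10.1.8).*

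This brings 8.7 into line with the standard already in 10.1 and 10.1.8 and with the qualifier in 8.10, and it supplies the missing cross-reference. New and worsened findings are still captured. The cost is one sentence, with no added procedure or data collection.
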